2 RATIONALE

Despite the availability of Genvoya, a single tablet once-daily fixed-dose formulation, a substantial number of individuals living with HIV infection still have difficulty swallowing whole tablets of ARV combinations. Therefore, crushed/dissolved tablet oral formulations are highly desirable as a potential strategy to overcome pill aversion. However, there is a theoretical concern that the systemic absorption of the active ingredients of the whole tablet formulation may be altered by crushing the tablets. We propose a study in healthy adult women and men research participants to determine whether Genvoya in crushed/dissolved form is bioequivalent with the whole tablet form.

The FDA recommended dosage of Genvoya is one tablet daily for the treatment of HIV infection (1). Since participants in this bioequivalence study will be dosed with Genvoya for only one dose on two occasions, we will only enroll healthy HIV-uninfected individuals in order to prevent the development of potential

viral resistance that could occur with this short-term drug exposure. In addition, healthy research participants are less likely to be using other medications that could affect the metabolism, absorption or elimination of the components of Genvoya and consequently interfere with the proposed study endpoints.

Genvoya was selected for this bioavailability study because this fixed combination InSTI-based therapy is included in the national treatment guidelines as a first line therapy for the treatment of HIV infection (8). Therefore, Genvoya is frequently prescribed for treatment-naïve patients initiating ART.

3 HYPOTHESIS and STUDY OBJECTIVE

3.1 Hypothesis

3.1.2 Genvoya crushed/dissolved tablet will be bioequivalent to the whole tablet.

3.2. Primary Objective

3.2.1 To investigate the bioequivalence of oral single whole tablet and crushed/dissolved tablet of Genvoya in healthy research participants by characterizing the plasma $AUC_{0-\infty}$ and C_{max} of EVG, COBI, FTC, TAV, and TFV after single doses of a whole and crushed/dissolved tablet of this fixed-dose ARV combination in healthy adult research participants.

3.3 Secondary Objective

3.3.1 To compare other pharmacokinetic parameters of oral single whole tablet and crushed/dissolved tablet of Genvoya in healthy adult research participants, T_{max} , and terminal elimination half-life, in plasma of EVG, COBI, FTC, TAF, and TFV.

4 STUDY DESIGN

The proposed bioequivalence study will have two pharmacokinetic observation periods:

Whole Tablet Period: Research participants will be asked to swallow a single whole Genvoya tablet under direct observation. The first 72-hour pharmacokinetic sampling period for each of the ARV components of Genvoya will occur as outlined in **Table 3**. Participants will return for a safety visit for clinical and laboratory assessments seven days after whole tablet dosing. A minimum 14 day washout period will take place between the whole tablet dosing and the crushed/dissolved tablet dosing.

Crushed/Dissolved Tablet Period: Research participants will be asked to swallow a single crushed/dissolved Genvoya tablet under direct observation. The second and final Genvoya pharmacokinetic sampling will occur as outlined in **Table 3**.

Pharmacokinetic Sampling. Plasma sampling for estimating pharmacokinetic parameters were selected to optimize information content of each sample for each drug (and TFV metabolite of TAF) for robust estimates of T_{max} , C_{max} , $AUC_{0-\infty}$, and terminal elimination half-life. These are based on prior observations of T_{max} and half-life.

Table 3. Pharmacokinetic sampling schedule

Sampling Hour	Pre-dose	0.25	0.5	0.75	1.0	1.5	2	3	4	5	6	10	14	24	48	72
EVG	x				x		x	x	x	x	x	x	x	x	x	x
COBI	x		x		x		x	x	x		x	x	x	x	x	x
FTC	x		x		x		x	x	x		x	x	x	x	x	x
TAF	x	x	x	x	x	x	x	x	x		x					
TFV	x	x	x	x	x	x	x	x	x		x	x		x	x	x

The proposed pharmacokinetic sampling visits will be conducted at the Drug Development Unit (DDU) in the Division of Clinical Pharmacology at the Johns Hopkins Hospital. The DDU staff has extensive experience conducting pharmacokinetic studies in healthy research participants. The DDU will provide study coordinators and other administrative research support, and recruit participants for this study.

Plasma samples will be processed and analyzed at the Clinical Pharmacology Analytical Laboratory (CPAL) within the Division of Clinical Pharmacology. Genvoya tablets will be donated by Gilead and will be stored and dispensed by the Johns Hopkins Investigational Pharmacy. Approximately 8ml of blood will be collected in each dosing period, on the time points outlined in **Table 3**. The plasma concentrations of EVG, COBI, FTC, TFV, and TAF will be quantified using validated liquid chromatographic-tandem mass spectrometric (LC-MS/MS) methods (UPLC-MS/MS). Assay validation reports are peer-reviewed and approved by the DAIDS-sponsored Clinical Pharmacology Quality Assurance program.

Safety Assessments. Safety will be assessed by monitoring physical examinations, vital signs, and laboratory and clinical adverse events. Safety laboratory tests will be performed at the two safety visits post dose with whole and crushed/dissolved Genvoya tablets. Laboratory tests will include hematology and chemistry. A negative HIV-1/2 Antigen/Antibody (Ag/Ab) screening test and negative hepatitis B surface antigen test in addition to chemistry, and hematology results as specified in the inclusion criteria section are required to meet study eligibility criteria.

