Procedures	Screening: Potential research participants provide written informed consent and undergo evaluation of inclusion and exclusion criteria. Whole Tablet Period (3 days): Research participants will swallow, under direct observation, a single dose of a whole Genvoya tablet, followed by plasma sampling for 72 hours as indicated in Table 1 below. Safety Visit: Participants will return approximately 7 days after the whole-tablet dosing for clinical and laboratory safety assessment visit. Washout: A minimum of 14 will elapse between the two Genvoya doses. Crushed/dissolved Tablet Period (3 days): Research participants will swallow, under direct observation, a single dose of a crushed/dissolved Genvoya tablet, followed by plasma sampling for 72 hours, as indicated in Table 1 below. Final Safety Visit: Participants will return approximately 7 days after the crushed/dissolved-tablet dosing for a final clinical and laboratory safety assessment visit. * Adverse events will be monitored at all study visits and graded using the DAIDS Adverse Events Grading Table (Version 2.1, July 2017) as outlined in the protocol.

Table 1: Pharmacokinetic Sampling Schedule

Sampling Hour	Pre-dose	0.25	0.5	0.75	1.0	1.5	2	3	4	5	6	10	14	24	48	72
EVG	x				x		x	x	x	x	x	x	x	x	x	x
COBI	x		x		x		x	x	x		x	x	x	x	x	
FTC	x		x		x		x	x	x		x	x	x	x	x	x
TAF	x	x	x	x	x	x	x	x	x		x					
TFV	x	x	x	x	x	x	x	x	x		x	x		x	x	x

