Genvoya is a category B drug for use during pregnancy (1). No adverse developmental effects were observed in animal studies when the components of Genvoya were administered separately during the period of organogenesis (1). TAF use in women during pregnancy has not been evaluated, while EVG, COBI, and FTC use during pregnancy has been evaluated in a limited number of women (1). Current data showed no birth defects reported for COBI or EVG and no difference in the overall risk of major birth defects for FTC compared with a U.S. reference population (1). It is unknown if COBI, EVG, and TAF are present in human breast milk; FTC has been shown to be present in human breast milk (1).

Clinical Pharmacology. The PK parameters of individual components of Genvoya are listed in **Table 2**. All PK parameter data are taken from the GenvoyaTM package insert for EVG, COBI, FTC, and TAF. Data for TFV, which results from the conversion of TAF, is taken from the VemlidyTM package insert with adjustment of PK parameters for 10 mg dose of TAF in Genvoya vs. 25 mg in Vemlidy, assuming dose proportionality (C_{max} , $AUC_{0-\infty}$, and C_{trough}) and the Genvoya package insert (TFV half-life only which differs significantly from TFV half-life when administered as TDF).

Table 2. Summary of Genvoya constituent drugs pharmacokinetic parameters after oral administration in HIV-infected adults. Mean (SD).

Parameter	Units	EVG	COBI	FTC	TAF	TFV (from TAF)
Dose	mg	150	150	200	10	NA
C_{max}	mg/mL	1.7 (0.4)	1.1 (0.4)	1.9 (0.5)	0.16 (0.08)	0.012
AUC_{0-∞}	mg/hr/mL	23.0 (7.5)	8.3 (3.8)	12.7 (4.5)	0.21 (0.15)	0.16
C_{trough}	mg/mL	0.45 (0.26)	0.05 (0.13)	0.14 (0.25)	NA	0.04
Half-life	hours	12.9	3.5	10	0.51	32

COBI and EVG are metabolized by CYP3A4 enzyme; therefore, concomitant use of these two drugs with CYP3A4 inhibitors could substantially increase their plasma concentration (1). COBI is also metabolized by CYP2D6. CYP3A4 inducers on the other hand, lower COBI and EVG plasma concentrations which may lead to loss of therapeutic effect of Genvoya and development of treatment failure and viral resistance (1). COBI is also an inhibitor of CYP3A4 and CYP2D6 in addition to drug transporters such as breast cancer resistance protein (BCRP), p-glycoprotein (P-gp), and organic anion transporting peptide (OATP) 1B1 and 1B3 (1). Therefore, co-administration of Genvoya with CYP3A4, CYP2D6, P-gp, BCRP, OATP1B1 or OATP1B3 substrates can significantly increase their plasma concentrations.

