APPENDIX

Table S1. Estimated fractional change of sequential samples relative to T_{max} during **rise before** and **decay after** C_{max} .

Drugs	PK Parameters		Sampling Hour															Samples relative to T_{max}		
	Half-life	Tmax	0.25	0.5	0.75	1	1.5	2	3	4	5	6	10	14	24	48	72	Before	After	Half-lives After
EVG	12.9	4				0.25		0.50	0.75	T_{max}	0.06	0.06	0.24	0.24	0.71	2.63	2.63	3	7	5.6
COBI	3.5	3		0.17		0.25		0.67	T_{max}	0.22		0.49	1.21	1.21	6.25	114.93	.	3	6	13.7
FTC	10	3		0.17		0.25		0.67	T_{max}	0.07		0.15	0.32	0.32	1.00	4.28	4.28	3	7	7.2
TAF	0.51	1	0.25	0.50	0.75	T_{max}	0.97	0.97	2.89	2.89	2.89	14.15	3	6	11.8
TFV	32	1.5	0.17	0.33	0.50	0.67	T_{max}	0.01	0.02	0.02		0.04	0.09	.	0.35	0.68	0.68	4	8	2.3

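### Minor: TFV could be assayed in the 14 h plasma already drawn, a cheap gain mainly for its half-life; separately, the schedules disagree on COBI at 72 h

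*Combined protocol and SAP*

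**What the plan says.** Section 4 gives the aim of the sampling: "Plasma sampling for estimating pharmacokinetic parameters were selected to optimize information content of each sample for each drug", so as to estimate Tmax, Cmax, AUC0-inf and half-life robustly. TFV AUC0-inf is a primary measure (Section 3.2.1) and TFV half-life a secondary one (Section 3.3.1).

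**TFV.** Footnote 5 of the Schedule of Events puts a 14 h draw in both periods. The TFV row of Section 4 Table 3, "TFV x x x x x x x x x x x x x x", carries 14 marks for 16 sampling times; the two blanks are 5 h and 14 h. The 14 h cell is also blank in the Schema's Table 1 and is a dot in Table S1. EVG, COBI and FTC are all marked at 14 h.

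**COBI.** The Section 4 Table 3 row, "COBI x x x x x x x x x x x x", has 12 marks, the last at 72 h. The Table 1 row, "COBI x x x x x x x x x x x", has 11, the last at 48 h. Table S1 ends its COBI row with "6.25 114.93 . 3 6 13.7": a dot at 72 h, 3 samples before the peak, 6 after, and 13.7 half-lives.

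**Half-lives.** Table 2, in the order EVG, COBI, FTC, TAF, TFV, reads "Half-life hours 12.9 3.5 10 0.51 32".

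**The concern.** TFV is the analyte whose terminal slope is hardest to estimate. It declines slowest, and sampling stops after little more than two half-lives. The fitted slope gives the half-life directly and supplies the extrapolated part of AUC0-inf. Plasma that could carry one more point on that slope is drawn and already sent for three other assays, and the protocol gives no reason for leaving TFV out.

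What is at stake is modest: the precision of a secondary endpoint, and some protection if a late sample is lost. Suppose the terminal phase begins between 10 and 14 h and the 48 h or 72 h value is missing. Only two terminal points then remain; a 14 h value would restore three.

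The COBI mismatch is a separate matter. The laboratory has two different instructions for one cell.

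**Working it through.** **Inputs.** Half-lives are from Table 2 and Tmax values from Table S1 (COBI 3 h, TFV 1.5 h). Sampling times are from Section 4 Table 3. The documents give no residual error, so I assume 10% on the log scale with a range of 5 to 15%, and mono-exponential TFV decline after the peak.

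**1. Reproducing Table S1.** Last sample divided by half-life:
- EVG 72/12.9 = 5.58 (stated 5.6)
- COBI 48/3.5 = 13.71 (13.7)
- FTC 72/10 = 7.20 (7.2)
- TAF 6/0.51 = 11.76 (11.8)
- TFV 72/32 = 2.25 (2.3)

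All five agree. The COBI figure agrees only with a last sample at 48 h.

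The TFV step from 10 to 24 h is 2^(14/32) − 1 = 0.354 (stated 0.35). A 14 h assay would split it into 2^(4/32) − 1 = 0.09 and 2^(10/32) − 1 = 0.24.

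**2. Precision of the TFV slope.** In a log-linear fit the standard error of the slope is proportional to 1/√Sxx, where Sxx = Σ(t − mean t)². The ratio with and without 14 h does not depend on the error size.

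| Points fitted without 14 h | Sxx without | Sxx with 14 h | Ratio of standard errors | Change |
|---|---|---|---|---|
| 24, 48, 72 h | 1152 | 2019 | √(1152/2019) = 0.755 | −24% |
| 10, 24, 48, 72 h | 2235 | 2715.2 | √(2235/2715.2) = 0.907 | −9% |
| 6 to 72 h (5 points) | 3080 | 3350 | 0.959 | −4% |
| 4 to 72 h (6 points) | 3733.3 | 3885.7 | 0.980 | −2% |
| All 8 after the peak | 4658.9 | 4704 | 0.995 | −0.5% |

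The first row applies only if the terminal phase begins after 10 h and by 14 h. If it begins after 14 h, the 14 h value is not used and the change is zero.

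**3. Half-life and AUC0-inf.** I simulated 40,000 profiles, using the linear trapezoid plus last concentration divided by slope. The table gives the standard deviation per participant and period, without → with 14 h.

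| Residual error | Points fitted without 14 h | ln half-life | ln AUC0-inf |
|---|---|---|---|
| 5% | 10 to 72 h | 0.049 → 0.045 | 0.0257 → 0.0257 |
| 5% | 24 to 72 h | 0.068 → 0.052 | 0.0271 → 0.0258 |
| 10% | 10 to 72 h | 0.099 → 0.090 | 0.0522 → 0.0520 |
| 10% | 24 to 72 h | 0.139 → 0.104 | 0.0560 → 0.0523 |
| 15% | 10 to 72 h | 0.152 → 0.137 | 0.0802 → 0.0795 |
| 15% | 24 to 72 h | 0.217 → 0.159 | 0.0900 → 0.0808 |

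The extrapolated share is 2^(−72/32) = 0.210 counted from dose, or 2^(−70.5/32) = 0.217 counted from the peak. It depends on the last sample, so a 14 h value does not alter it. Trapezoid bias across the 10 to 24 h gap is also negligible, at about 0.16% of AUC0-inf without the 14 h value and 0.06% with it.

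**4. COBI at 72 h.** (72 − 3)/3.5 = 19.7 half-lives after the peak, leaving 2^(−19.7) ≈ 1.2 × 10⁻⁶ of Cmax. At 48 h the fraction is 2^(−45/3.5) ≈ 1.3 × 10⁻⁴.

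**The case against.** The strongest reply is that TFV is already well sampled. Table S1 gives it 8 samples after the peak, more than any other analyte, and 10, 24, 48 and 72 h can support a slope. The 14 h blank is the same in all three tables, one of which sets out sample spacing, so it may be deliberate. The expected fall from 10 to 14 h, a step of 0.09, is about the size of the assumed residual error. This stands, and it is why the point is an improvement and not an error in the plan.

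The lost-sample argument is also narrower than it looks. Under Section 11, missing a sampling visit window stops further dosing, so a miss in the first period removes the participant whatever is assayed at 14 h. The protection applies mainly to the second period. If 10 h is already terminal, losing 48 h or 72 h still leaves three points without 14 h.

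A reader might infer that the COBI mark at 72 h is taken at the expense of TFV. The documents do not support that: TFV is itself marked at 72 h in every schedule, and the COBI cell takes nothing from it. A reader might also infer that the TFV slope is inadequate or that TFV AUC0-inf is compromised by the gap. The sample count and the simulation do not bear that out.

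**Conclusion.** The point holds as a minor, cheap improvement. Assaying TFV at 14 h lowers the slope's standard error by about 9% if decline is terminal by 10 h, and by up to 24% if the terminal phase starts between 10 and 14 h. The gain is 4% or less when points from 6 h or earlier are also used, and nil if the phase starts after 14 h. The documents do not say when it starts, so 24% is a best case and should not be quoted alone. The benefit goes to TFV half-life and, in limited circumstances, to keeping a three-point slope.

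It would be too strong to say that the primary TFV comparison is at risk, since the precision of AUC0-inf hardly moves. The larger TFV limitation, sampling that ends at about 2.25 half-lives with roughly 21% of AUC0-inf extrapolated, is untouched by this change.

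The ratios of standard errors rest on log-linear decline within the fitted window. The half-life and AUC figures also rest on the assumed 5 to 15% residual error and a 32 h half-life.

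The COBI inconsistency is certain, but it is only a consistency correction: on the plan's own half-life, the 72 h assay carries no information.

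**What to change.** 1. Mark TFV at 14 h in the Schema's Table 1, in Section 4 Table 3 and in Table S1. In Table S1, replace the 10 to 24 h step of 0.35 with 0.09 and 0.24, and raise the count after the peak from 8 to 9.
2. State in Section 13.1 how terminal-slope points are chosen, so that a 14 h value before the terminal phase is left out by rule. At present that section says only that the analysis is non-compartmental.
3. Separately, make COBI at 72 h agree across the three tables. Removing the mark from Section 4 Table 3 would match Table 1 and the counts in Table S1, and would lose no information.

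**Cost.** One extra TFV assay per participant per period: 12 × 2 = 24 for the planned completers, and at most 20 × 2 = 40 if all 20 were enrolled and dosed twice. There is no extra draw, visit or blood volume. Removing COBI at 72 h would save the same number of COBI assays, but the documents give no assay costs, so I do not claim that the two cancel out.

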Participants who satisfy the inclusion criteria will be asked to return to the DDU on Day 1. Individuals will be given a single oral dose of Genvoya whole tablet (Whole Tablet Period) or a crushed/dissolved Genvoya tablet mixed in water (crushed/dissolved Tablet Period) under direct observation. They will undergo pharmacokinetic sampling at the DDU for the components of Genvoya as outlined in **Table 2** (Pharmacokinetic sampling schedule) and **Table 3** (Schedule of Events). Approximately 8 mL will be collected at all pharmacokinetic time points. Serum creatinine will be collected once, pre-dose, for estimated creatinine clearance. Female participants will have a POCT qualitative urine pregnancy test prior to dosing and negative test results are required for participants to continue with dosing/the study visit. Any positive POCT qualitative urine pregnancy test results will be confirmed with a serum quantitative pregnancy test.

At entry, all signs, symptoms, and diagnoses within 30 days prior to entry will be recorded, including actual and estimated dates of onset and resolution. After entry, all new diagnoses,

signs and symptoms will be recorded at the visit they are reported and should include status, date of onsent, date of discovery and date of resolution, if applicable.

For the WholeTablet Period, subjects will be given a single oral dose of a whole Genvoya tablet under direct observation. Participants will be asked to return to the DDU approximately 7 days after receiving the whole tablet dose, in order to complete the first study safety evaluation. Participants will be required to undergo a minimum 14-day washout period following receipt of the Genvoya whole tablet.

For the Crushed/Dissolved Tablet Period, subjects will be given a single oral dose of a crushed/dissolved Genvoya tablet under direct observation. The solution of crushed/dissolved Genvoya tabled mixed in water will be prepared at the Johns Hopkins Investigational Drug Pharmacy. Participants will be asked to return to the DDU approximately 7 days after receiving the crushed/dissolved tablet dose, in order to complete the final study safety evaluation.

Table 3. Schedule of Events

Evaluations	¹Screening	Whole Tablet Period²					Safety Visit	Crushed/Dissolved Tablet Period²				Safety Visit
	Visit 1	Visit 2	Visit 3	Visit 4	Visit 5	Visit 6	Visit 7	Visit 8	Visit 9	Visit 10	Visit 11	
	Day -30	Day 1	Day 2	Day 3	Day 4	Day 8	Day 1	Day 2	Day 3	Day 4	Day 8	
Informed Consent	X											

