Vital Signs (BP, HR, Temp)	X	X	X	X	X	X	X	X	X	X		
Weight	X	X					X				X	
Height	X											
HIV-1/2 Ag/Ab	X											
HBsAg	X											
CBC w/ Diff	X										X	
Complete Metabolic Panel	X	X²				X	X²				X	
Serum Phosphorus	X					X					X	
POCT Qualitative Urine HCG (female participants only)	X	X					X					
³Estimated Creatinine Clearance	X	X					X				X	
Medical /Medication History	X											
Physical Exam	X											
Adverse Event Assessment		X	X	X	X	X	X	X	X	X	X	
Concomitant Medications		X	X	X	X	X	X	X	X	X	X	
Targeted Physical Exam⁴		X	X	X	X	X	X	X	X	X	X	
Observed whole dose Genvoya		X										
Observed crushed/dissolved dose Genvoya							X					
Plasma Pharmacokinetics⁵		X	X	X	X		X	X	X	X		

¹Screening within 30 days of entry

²Serum creatinine only

³Creatinine Clearance estimated by Cockcroft-Gault formula

⁴A targeted physical exam will only be completed if clinically indicated

⁵Pharmacokinetic sampling time points pre-dose and 0.25, 0.5, 0.75, 1, 1.5, 2, 3, 4, 5, 6, 10, 14, 24, 48, and 72 hours after each dose. There is a +/- 5 min window for 0.25hr to 1.5hr PK specimen collection and a +/- 15 min window for 2hr to 14hr PK specimen collection. Windows for 24, 48 and 72 hr PK specimen collection outlined in section 9.2.3-9.2.5.

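### Assay EVG, COBI and FTC in early samples the plan already draws: cheap cover against an earlier crushed-tablet peak, with a small effect on Cmax and the main gain in Tmax

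*Combined protocol and SAP*

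**What the plan says.** Section 3.2 makes Cmax co-primary with AUC for every analyte: "by characterizing the plasma $AUC_{0-\infty}$ and C_{max} of EVG, COBI, FTC, TAV, and TFV". Section 3.3 makes Tmax secondary for the same five.

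Footnote 5 to the Schedule of Events lists one set of draws for both periods: "sampling time points pre-dose and 0.25, 0.5, 0.75, 1, 1.5, 2, 3, 4, 5, 6, 10, 14, 24, 48, and 72 hours". Section 9.2.2 adds: "Approximately 8 mL will be collected at all pharmacokinetic time points".

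The sampling schedule (Table 1 in the Schema, Table 3 in Section 4) then selects which analytes are measured in each sample. Up to 2 h after dosing:

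| Analyte | Assayed at (h) | Drawn but not assayed (h) |
|---|---|---|
| EVG | 1, 2 | 0.25, 0.5, 0.75, 1.5 |
| COBI, FTC | 0.5, 1, 2 | 0.25, 0.75, 1.5 |
| TAF, TFV | 0.25, 0.5, 0.75, 1, 1.5, 2 | none |

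Section 4 gives the basis for the times: "These are based on prior observations of T_{max} and half-life". Table S1 in the Appendix shows the check that was made. It takes one Tmax per analyte (EVG 4 h, COBI and FTC 3 h) and counts the samples before and after it.

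**The concern.** The trial exists because crushing may alter absorption (Sections 1.1 and 2), and the test form is swallowed mixed in water. A schedule built around one earlier Tmax per analyte does not allow for the test form peaking at a different time. If the crushed peak comes early, few EVG assays precede it, or none. An observed maximum at the first post-dose assay then gives no evidence that concentrations had risen to it.

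Apart from assay noise, a sampled maximum cannot exceed the true one. An early peak that falls between assays therefore lowers the observed crushed Cmax and misplaces Tmax. If the true Cmax ratio were near 1.25, a downward bias would make a false finding of equivalence slightly more likely. The plasma that would settle the matter is already drawn and goes to the same laboratory.

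**Working it through.** **1. The plan's own count.** Counting assay times before the Table S1 Tmax gives EVG 3 (1, 2, 3 h), COBI and FTC 3 each (0.5, 1, 2 h), TAF 3 and TFV 4. All five agree with Table S1.

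**2. The same count for an assumed earlier crushed peak.** The last two columns add the assays proposed below.

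| Peak at | EVG, plan | COBI/FTC, plan | EVG, with additions | COBI/FTC, with additions |
|---|---|---|---|---|
| 1 h | 0 | 1 | 2 | 2 |
| 1.5 h | 1 | 2 | 3 | 3 |

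**3. Spacing in hours.** EVG is assayed hourly from 1 to 6 h. COBI and FTC are 0.5 h apart from 0.5 to 1 h, 1 h apart from 1 to 4 h, and 2 h apart from 4 to 6 h. Between assays, the early spacing is no wider than around the whole-tablet peak. The shortfall is in samples before an early peak.

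**4. Worst case for a single profile.** The model is one-compartment: C(t) = ka/(ka − ke) × [exp(−ke·t) − exp(−ka·t)], with ke = ln 2 / half-life (Table S1: 12.9, 3.5 and 10 h) and ka solved from Tmax = ln(ka/ke)/(ka − ke). For a peak at 1.5 h the planned schedule reads the 2 h value:

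- EVG: ke 0.0537, ka 2.65; C(1.5) = 0.9226, C(2) = 0.9116; loss 1.2%.
- COBI: ke 0.198, ka 1.58; 0.7430 and 0.7210; loss 3.0%.
- FTC: ke 0.0693, ka 2.44; 0.9013 and 0.8882; loss about 1.4%.

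Over an assumed crushed Tmax of 0.4 to 2 h, the largest losses are 2.8% for EVG (Tmax 0.4 h, read at 1 h), 4.0% for COBI (about 1.4 h) and 2.1% for FTC (about 1.4 h). With the added assays they are about 0.5%, 1.3% and 0.7%.

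**5. Average bias in the crushed/whole Cmax ratio.** Simulation of 40,000 profiles per arm, with the whole-tablet median Tmax from Table S1 and assumed log-scale spreads of 0.35 in Tmax and 0.2 in half-life. Values are observed ratio divided by true ratio on the planned schedule.

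| Crushed median Tmax | EVG | COBI | FTC |
|---|---|---|---|
| 0.75 h, no noise | 0.992 | 0.996 | 0.999 |
| 1 h, no noise | 0.996 | 0.994 | 0.998 |
| 1.5 h, no noise | 0.997 | 0.994 | 0.997 |
| 0.75 h, 8% noise | 0.967 | 0.984 | 0.995 |
| 1 h, 8% noise | 0.975 | 0.982 | 0.993 |
| 1.5 h, 8% noise | 0.984 | 0.982 | 0.993 |

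The whole-tablet Cmax is under-read as well, so the biases partly cancel in the ratio. The 8% is an assumption, since the documents give no assay precision. Part of the effect under noise arises because more samples near a peak raise its observed maximum.

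**6. Effect on the equivalence decision.** Take a 0.7% bias, near the top of the noise-free range. The true ratio of 1.25 is then read as 1.25 × 0.993 = 1.241. For 12 pairs, the 90% interval (mean ± 1.796 × s/√12 on the log scale) must lie within ±ln 1.25 = ±0.223. It does so with probability 6.0% at SD 0.25 and 6.8% at SD 0.15 (both SDs appear in Table 4), against 5.0% without bias.

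**7. Tmax.** Mean absolute error without noise, planned schedule against added assays: at a crushed median of 1.5 h, about 0.25 h against 0.14 h for all three analytes; at 0.75 h, EVG 0.29 h against 0.08 h. The whole-tablet error is 0.28 to 0.33 h. With 8% noise, EVG at 0.75 h goes from 0.90 to about 0.48 h, and COBI at 1.5 h from 0.42 to 0.35 h.

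**8. Sensitivity to a sharp peak.** With an assumed two-compartment shape (80% fast phase, distribution half-life 0.5 or 1 h), the planned schedule loses about 5% of EVG Cmax at a Tmax of 0.7 h and 10 to 24% at about 0.45 to 0.6 h.

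**The case against.** The strongest reply is that nothing in the documents says crushing brings the peak forward. Section 1.1 says only that absorption may change. The one crushed-tablet study it cites found COBI and FTC concentrations comparable and TAF AUC 20% lower, and Section 5 has the dose taken with a light meal. The plan states its rationale and shows its check. COBI and FTC already have a 0.5 h assay. A shift from 3 or 4 h to 1.5 h is 1.5 to 2.5 h, which a 0.25 h error would not hide. At that median the gain is 0.25 − 0.14 = 0.11 h, under 7 minutes, close to the permitted draw windows of 5 and 15 minutes. All of this stands, and it is why the point ranks low.

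Two stronger readings are tempting and should be resisted. A reader might infer that sampling is densest at the whole-tablet peak and thinner where the crushed form may peak. Between assays, measured in hours, that is not so (step 3). A reader might also apply a worst-case loss of 3% or more to every crushed profile and infer false-equivalence rates in double figures. That ignores the matching loss in the whole-tablet arm. A 3% average bias arises only for EVG, with an assumed 8% noise and a 0.75 h median. The risk of false equivalence further requires a true ratio near 1.25, and nothing in the documents suggests one.

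The reply does not remove the EVG gap. With a first post-dose assay at 1 h, the study could not recognise a peak at or before that time.

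**Conclusion.** The point holds as a cheap, low-severity improvement. EVG, COBI and FTC are left unmeasured in early plasma that the plan already draws, and the schedule rests on one earlier Tmax per analyte. The cost to the primary Cmax comparison is small: under 1% on average without noise, about 3% at most with the assumed 8% noise, and a false-equivalence rate of about 6 to 7% instead of 5% at a 0.7% bias. The gain lies mainly in the secondary Tmax comparison and in protection against a sharp early EVG peak.

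The sizes depend on an earlier crushed peak, the one-compartment shape, the spreads and the noise level. All of these are assumptions; only the half-lives and whole-tablet Tmax values come from the documents. If the crushed dose peaks when the whole tablet does, the added assays change little.

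**What to change.** In Table 1 and in the sampling schedule in Section 4 (Table 3), mark EVG for assay at 0.5, 0.75 and 1.5 h as first priority, and COBI and FTC at 0.75 and 1.5 h. Do this identically in both periods, on samples already drawn, and update Table S1 to match.

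Cost: 3 + 2 + 2 = 7 extra results per participant per period, so 7 × 2 × 12 = 168 for 12 completers (280 if all 20 enrolled supplied both periods). The Section 4 schedule already asks for 12 + 12 + 12 + 10 + 14 = 60 results per period, so this is about 12% more. There is no added draw or visit. Plasma volume should not be an obstacle, because all five analytes are already measured from single draws at 1, 2, 3 and 4 h.

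There is one statistical downside. With assay noise, more samples near an early peak can raise the observed crushed maximum. At the assumed 8% noise, this would bias the Cmax ratio upward by about 1 to 2%. An EVG peak before 0.5 h would still have no earlier assay.
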